2.4.2 Statistical hypothesis, model, and method of analysis

A Poisson distribution will be assumed for the number of participants with composite efficacy failures. Specifically, the number of composite efficacy failure events in group *i* will be assumed to follow a Poisson distribution, i.e., $y_i \sim \text{Poisson}(\mu_i)$, where μ_i is the expected number of events in group *i*, with $\mu_i = \lambda_{i,T} t_{i,T}$, with $t_{i,T}$ being the total on-treatment time in group *i* in years up to T = 12 months, thus incomplete follow-up of participants due to early discontinuation is adjusted for. The follow-up time will be calculated as [min(upper limit of the Month 12 visit window, date of treatment discontinuation, date of lost-to-follow-up) – date of randomization]. The probability of a composite event occurring before *T* can the be derived as $\theta_i = 1 - \exp(-\lambda_{i,T})$.

For the purposes of analysis, time of discontinuation of study drug will be determined by the date of last study drug administration as follows:

- Arm 1: earliest date of discontinuation of study drug (TAC or MMF)
- Arms 2 and 3: CFZ533 study drug discontinuation date + 14 days to account for the dosing interval.

Novartis	For business use only	Page 22
SAP		CCFZ533A2202

The exposure-adjusted treatment difference in composite efficacy failure rates between a CFZ533 arm and Control at Month 12 will then be evaluated as for the primary estimand.

Specifically, a CFZ533 arm will be considered successful if the annualized composite efficacy failure rate difference between this CFZ533 arm and the Control arm is less than 15% with probability greater than 80%:

$$P(\theta_{\rm CFZ533} - \theta_{\rm control} < 0.15 | data) > 0.8$$

The required posterior probabilities will be estimated from simulations of the posterior distributions of $\theta_{CFZ533} - \theta_{control}$ and compared to the threshold for the level of proof. The prior distributions of $\lambda_{i,T}$ will be assumed to be non-informative (specifically, Gamma(0.001, 0.001)). The posterior mean composite efficacy failure rates for each treatment arm and for the difference in mean response rates between CFZ533 treatment arms and control will be presented together with 95% credible intervals.

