3.2 Power for primary endpoint

The sample size justification considers the probability of success of the study based on the success criterion for the planned sample size. The success criterion for one CFZ533 treatment arm (see Section 2.4.2) is reached if

$$P(\theta_{\rm CFZ533} - \theta_{\rm control} < 0.15 | data) > 0.8,$$

[figure not shown]
where θ is the composite efficacy failure rates, and the prior is Beta(1/3, 1/3).

Table 3-2 and Figure 3-2 show the probability of success of the study for a sample size of 48 participants in the CFZ533 arm and 32 participants in the control arm for a range of underlying event rates for composite efficacy failure and serious infections in the CFZ533 treatment arm and in the control arm. A control rate of 10% at Month 12 is expected based on (Levitsky et al 2017), which examined a large registry of deceased donor liver transplant participants from Scientific Registry of Transplant Recipients (SRTR) and internal Novartis studies (RAD001 Study H2304 and AEB071 Study B2203).

of CFZ533 arm and 32 participants of control arm			
$\theta_{ m CFZ533}$	$ heta_{ ext{control}}$	Probability of success	
0.07	0.070	0.971	
0.07	0.103	0.986	
0.07	0.135	0.993	
0.07	0.168	0.997	
0.07	0.200	0.999	
0.11	0.070	0.833	
0.11	0.103	0.904	
0.11	0.135	0.947	
0.11	0.168	0.973	
0.11	0.200	0.987	
0.15	0.070	0.594	
0.15	0.103	0.729	
0.15	0.135	0.830	
0.15	0.168	0.900	
0.15	0.200	0.944	

Table 3-2Probability of success under different event rates for 48 participants
of CFZ533 arm and 32 participants of control arm

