* For all Month 12 analyses, the end of visit window of Month 12 visit is Day 358, instead of Day 372.

Under this window schema, multiple records of a participant are re-aligned into the same visit as follows:

- For post-randomization continuous values (except for CFZ533, TAC, and MMF trough level measurements and liver tests), for a given participant, if multiple numeric measurements for a given variable are reported in the same visit window (e.g., Month 6), then the measurement closest to the target visit day will be taken; if tie, take the earlier measurement. For screening visit, the target day is day of transplant – 1; for baseline, day of transplant; for randomization, start of study drug (Day 1); for other visits, the midpoint of the visit window.
- For trough levels, the last value observed within a visit window is taken.

- For liver tests (bilirubin, SGOT, SGPT, GGT, and alkaline phosphatase), the following algorithm is applied:
 - a. If an acute rejection occurs within a visit window with multiple liver tests reported, the time of the event is the date rejection first suspected, and the liver test to be summarized are the closest to that event (if tie, take the earlier one)
 - b. If no rejection occurs, the assessment closest to the target day is taken.
- For categorical values, the worst value of all records observed in the visit window is used.

For parameters which are not collected at every scheduled visit

, visit windows defined in Table 5-1 will be combined using the following rules for an applicable visit post randomization: "lower limit" of the combined window= "upper limit of prior applicable visit" + 1, "upper limit" of the combined window = "target day of current visit" + integer part of [("target day of next applicable visit" – "target day of current visit")/2]. For example, if a parameter is measured only at Randomization, Day 29 (Month 1), Month 3, Month 6, and Month 12, the combined Day 29 (Month 1) visit window will be from Day 2 to Day 50 (= Day 22 + interger part of [(78 - 22)/2]), Month 3 will extend from Day 51 to Day 120 (= Day 78 + interger part of [(162 - 78)/2]), etc.. If more than one assessment falls into the combined window, the rules defined above handling multiple records are applied.

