5.5.1 Exposure-adjusted incidence rate and 100(1 - α)% confidence interval

Exposure-adjusted incidence rates is presented per 100 participant-years. Participant-years is calculated as a sum of individual participant durations in days divided by 365.25.

It will be assumed that for each of *n* participants in a clinical trial the time t_j , (j = 1, ..., n) to the first occurrence of a certain treatment emergent event is observed, or if the event was not experienced, the (censored) time to the end of the observation period or EOT, whichever occurs earlier. The sequence of first occurrences of an event will be modeled to follow approximately a Poisson process with constant intensity θ . The rate parameter θ will be estimated as $\lambda = D/T$, where $T = \sum_{j=1}^{n} t_j$ and D is the number of participants with at least one event. Conditionally on T, an exact $100(1 - \alpha)\%$ confidence interval for a Poisson variable with parameter θT and observed value D can be obtained based on (Garwood, 1936), from which an exact $100(1 - \alpha)\%$ confidence interval for $\lambda = D/T$ will be derived as follows (Sahai, 1993; Ulm, 1990):

Lower confidence limit
$$L = \frac{0.5\chi_{\frac{\alpha}{2},2D}}{T}$$
 for $D > 0$, and $= 0$ otherwise;

Upper confidence limit $U = \frac{0.5\chi_{1-\frac{\alpha}{2},2D+2}}{T}$.

where $\chi_{\alpha,k}$ is the α -th quantile of the Chi-square distribution with k degrees of freedom.

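### The Gamma(0.001, 0.001) prior in SAP 2.4.2 is not non-informative when an arm has very few failures: with none, the 95% credible interval collapses to zero

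*SAP*

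**What the plan says.** SAP 2.4.2 models the number of composite failures in each arm as Poisson, with exposure "being the total on-treatment time in group *i* in years up to T = 12 months". The rate λ is converted to a 12-month probability by θ = 1 − exp(−λ). The priors on λ "will be assumed to be non-informative (specifically, Gamma(0.001, 0.001". Posterior means for each arm and for the difference "will be presented together with 95% credible intervals". The decision rule is separate from the intervals: the annualised failure-rate difference between this "CFZ533 arm and the Control arm is less than 15% with probability greater than 80" per cent.

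Protocol 12.4.2 asks only for non-informative priors. The design calculation in SAP 3.2 is binomial "and the prior is Beta(1/3, 1/3". SAP 2.4.4 plans no sensitivity analysis, and no section says how an arm with no failures is to be reported.

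**The concern.** A Gamma prior with shape 0.001 adds almost nothing to the event count. That is harmless when the count is moderate. When the count is zero, the posterior shape is 0.001 and nearly all its mass lies at zero. The prior then makes a strong statement, that the arm carries no risk, on the evidence of about 30 people without an event.

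The control arm is where this could happen. It has 32 participants and an expected failure rate of 10%, so about 3 events. If it had none, the report would show a control rate of 0 with an interval of 0 to 0. The interval for the difference would carry no control-arm uncertainty, so a handful of CFZ533 failures could read as an established excess.

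**Working it through.** **Inputs.** The prior is Gamma(a, b), read as shape and rate, with a = b = 0.001 (SAP 2.4.2). Arm sizes are 48 and 32, and the expected control rate is 10% (SAP 3.2). For Month 12 analyses "the end of visit window of Month 12 visit is Day 358, instead of Day 372" (SAP 5.1), so 32 controls contribute at most about 31 person-years. Only on-treatment time counts and the study was terminated early. Actual exposure is not in the documents, so I assume 20 to 32 control person-years.

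**Plan's own figure.** Exact enumeration of the binomial rule with Beta(1/3, 1/3) reproduces all 15 cells of SAP Table 3-2 to within 0.001 (for example 0.904 at failure rates of 0.11 and 0.103). The documents give no figure for interval behaviour under the Gamma prior.

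**Posterior.** With y failures in t person-years, λ is Gamma(y + a, t + b). Its 2.5% and 97.5% quantiles are transformed by θ = 1 − exp(−λ).

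**Zero failures.** Upper 95% limit for θ at 32 person-years:

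| Method | Upper limit |
|---|---|
| SAP prior | 1.8 × 10⁻¹³ |
| Shape 1/3 | 0.061 |
| Shape 1/2 | 0.076 |
| Exact Poisson (formula in SAP 5.5.1) | 0.109 |

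Beta(1/3, 1/3) with 0 of 32 also gives 0.061.

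The chance of no control failures at a true 10% rate is exp(−0.1054 t), since −ln 0.9 = 0.1054. That is 3.4% at 32 person-years, 5.2% at 28 and 12.2% at 20. At 7%, the lowest control rate in Table 3-2, it is 9.8%, 13.1% and 23.4%.

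**Difference, 3 failures in 42 versus 0 in 28 person-years.**

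- SAP prior: 0.015 to 0.158.
- Shape 1/3: −0.015 to 0.160.
- Shape 1/2: −0.027 to 0.162.

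The first interval is simply the CFZ533 arm's own interval. The Gamma(3) quantiles 0.619 and 7.225, divided by 42, are 0.0147 and 0.172, which transform to 0.015 and 0.158. Control contributes nothing.

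**One or more failures, 32 person-years.**

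| y | SAP prior | Shape 1/2 | SAP width relative to shape 1/2 |
|---|---|---|---|
| 1 | 0.001 to 0.109 | 0.003 to 0.136 | 18% narrower |
| 3 | 0.019 to 0.202 | 0.026 to 0.221 | 6% narrower |
| 5 | width 0.224 | width 0.232 | 3% narrower |

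Both limits move down. For y ≥ 1 the lower limit matches the exact Poisson lower limit, and the upper limit matches the exact upper limit for y − 1 events.

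**Coverage of the 95% interval for one arm (exact Poisson sums).** Averaged over true 12-month rates of 5% to 20%:

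| Person-years | SAP prior | Shape 1/2 |
|---|---|---|
| 20 | 86.5% | 95.4% |
| 28 | 90.5% | 95.0% |
| 32 | about 92% | 94.8% |

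At 28 person-years shape 1/3 averages 93.8%. The SAP upper limit there is too low 7.9% of the time, against 2.4% with shape 1/2 and a nominal 2.5%.

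Pointwise results vary:

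- True 10%, 32 person-years: 94.4% for all three priors.
- True 10%, 28 person-years: 93.7% (SAP) against 91.7% for either alternative.
- True 10%, 20 person-years: 85.8% (SAP and shape 1/3) against 97.9% (shape 1/2).
- True 5%, 32 person-years: 79.9% (SAP) against 97.4% (shape 1/2).
- True 13.5%, 32 person-years: 92.5% (SAP) against 97.0% (shape 1/2).

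**Decision rule.** At 42 and 28 person-years, the largest CFZ533 failure counts that pass with 0 to 6 control failures are 5, 6, 7, 8, 10, 11, 12 under the SAP prior. Shapes 1/3 and 1/2 give the same counts except 13 at six control failures. At 48/32, 40/26 and 30/20 person-years, with 0 to 4 control failures, the SAP boundary is the same or one event lower.

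**The case against.** A reader might infer that the control-arm intervals are too narrow in general. The figures do not support that. At the planned rate with 28 to 32 person-years, coverage equals or exceeds that of the proposed replacements. At the expected 3 events the interval loses about 6% of its width, and its lower limit falls as well. The averaged deficit comes mostly from rates below plan. Some remains above plan (89.0% at 13.5% and 28 person-years), and low exposure makes it worse. This part of the objection stands.

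A reader might also infer that the prior makes success easier. It does not: the passing boundary is unchanged or one event stricter.

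Two further objections carry some weight. SAP 5.5.1's "confidence interval for a Poisson variable with parameter" and its rate serves exposure-adjusted incidence of treatment-emergent events, and exact limits are conservative. It is therefore only a reference here, and the case rests on shapes 1/3 and 1/2. The change would also come after an open-label interim analysis and termination, which is an awkward time to alter a primary prior. The fix allows for this.

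None of this answers the zero-failure case. SAP 2.4.5 plans summaries of the composite and its components, so a zero count would be visible, but the credible intervals printed for it would still be wrong.

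**Conclusion.** The point holds in limited form. The prior is strongly informative when an arm has no failures and noticeably so at one. It matters little at three or more unless the true rate or the exposure is low. With no control failures, the reported control interval is effectively a point at zero, and the difference interval can exclude zero where shape 1/3 or 1/2 would include it. The chance of that control count is 3% to 12% at the planned 10% rate, and 10% to 23% at 7%.

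These sizes rest on assumed exposures of 20 to 32 person-years in control (28 against 42 in the worked example), a constant event rate, and an averaging range of 5% to 20% that I chose. What is affected is the reported estimates and intervals. The 15%/80% conclusion is essentially untouched.

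**What to change.** In SAP 2.4.2, for the reported posterior means and 95% credible intervals, use Gamma(0.5, 0.001) for each arm's rate. Gamma(1/3, 0.001) is the alternative if consistency with the Beta(1/3, 1/3) design prior is preferred; its average coverage is slightly lower. If the sponsor would rather keep the primary prior after the open-label interim analysis, report these intervals alongside it and state that they are the ones to use whenever an arm has no failures.

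The programming cost is one prior parameter. The statistical cost is that each arm's posterior mean rises by up to half an event: 0.5/28 = 1.8 per 100 person-years in control and 0.5/42 = 1.2 in CFZ533. This moves the difference slightly in favour of CFZ533. If the new prior were also used for the decision rule, it could raise the passing CFZ533 count by one event in some configurations. The SAP should say so.

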2.4.3 Handling of missing values/censoring/discontinuations

Participants continued to be followed until Month 12 visit, early study drug discontinuation, or lost to follow-up, whichever first. If no event is observed, the partcipant is considered as censored and will still contribute to the analysis as described above.

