12.4.4 Supportive analyses

As a supportive analysis, a Poisson distribution rather than binomial will be applied for the number of subjects with composite failures. Specifically, the number of composite efficacy failure events in group *i* will be assumed to follow a Poisson distribution , i.e., $y_i \sim \text{Poisson}(\mu_i)$, where μ_i is the expected number of events in group *i*, with $\mu_i = \lambda_{i,T} * t_{i,T}$, $t_{i,T}$ being the total follow up time in group *i* in years, thus incomplete follow up of subjects due to early discontinuation is adjusted for. The follow up time will be calculated as [Treatment start date – min (lower limit of the Month 12 visit window, lost-to-follow-up date)].

For the purposes of analysis, time of discontinuation of study drug will be determined by date of last study drug administration as follows:

- Arm 1: earliest date of discontinuation of study drug (TAC or MMF)
- Arms 2 and 3: CFZ533 study drug discontinuation date + 14 days to account for the dosing interval

If a subject discontinues before randomization, the rules of Arm 1 apply.

The exposure-adjusted treatment difference in composite efficacy failure rates between a CFZ533 arm and control at Month 12 will then be evaluated as for the primary endpoint.

In addition, Kaplan-Meier estimates of time to composite efficacy failure and BPAR censored at Month 12 will be respectively constructed and presented graphically. In this analysis, subjects who have not experienced composite efficacy failure, are lost to follow-up, or do not attend the Month 12 visit after treatment discontinuation will be censored with the censoring time defined by the last contact day.

Impact of COVID-19 or any other pandemic on the primary endpoint will be assessed. Details will be presented in SAP.

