2.1 Data analysis general information

Due to the early termination of the study, the analysis plan has been modified and may be different from the Protocol.

The primary analysis will be performed after all participants have completed the Month 12 visit, or prematurely discontinued study before Month 12. These analyses will be performed by a Contract Research Organization, ICON. Interim analyses, detailed in Section 2.13, will be performed also by ICON.

The following general data conventions will apply:

- Cut-off day is defined as the latest study day before or up to which data will be used in the • analysis. Note that safety data collected during the Safety Follow-up period after EOS is reported to Novartis/Safety and will be included in relevant analyses.
- Descriptive statistics will be calculated based on observed values. Missing values will be • presented separately for each parameter or category. Categorical data will be presented as frequencies and percentages. For continuous data, n (sample size), mean, standard deviation, median, 25th and 75th percentiles, minimum, and maximum will be presented.
- BPAR will be based on centrally blinded adjudicated data. All other efficacy • endpoints will also be based on central

lab data.

- AE, SAE, Infection, Serious Infection (including malignancies), CMV information, and • EBV information will be summarized based on all eligible collected events.
- All lab and vital sign tables will include data since baseline (liver Tx) but changes are calculated based on the day of randomization. All summaries are based on central lab data.

Novartis	
SAP	

- Efficacy and liver function analyses are based on all available data including those after study medication discontinuation or as a supportive analysis based only on on-treatment values. Participants are censored for the time-to-event analyses if they do not have an event. For on-treatment analysis, the censoring day is the date of discontinuation of study treatment (defined in Section 2.1.1); for the all-data analysis (regardless of on-treatment or off-treatment), the censoring day is the last contact day.
- Listings will only be provided for variables explicitly indicated in this SAP. Listings will include all available data.

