2.4.1 Primary endpoint

The primary efficacy endpoint is occurrence of composite efficacy failure (BPAR, graft loss, or death) at 12 months post-transplantation based on central pathologist evaluation (graft loss and death will be from local evaluation). The estimand is:

- Population: defined through appropriate inclusion/exclusion criteria to reflect the targeted population.
- Endpoint: composite efficacy failure at Month 12 post-transplantation, defined as BPAR, graft loss, or death.
- Treatment of interest: the randomized treatment, CFZ533 300 mg + MMF, CFZ533 600 mg + MMF, and TAC+MMF, regardless of treatment or study discontinuation, loss to follow-up, ascites-based dosing adjustment, or administration of CS (treatment policy).
- Summary measure: the difference in the proportion of participants with composite efficacy failure in CFZ533 arms at 12 months post-transplantation as compared to control.

BPAR is defined as an acute rejection confirmed by biopsy within 48 hours of the suspected rejection (preferably within 24 hours) with a rejection activity index (RAI) score \geq 3. Events of rejection which were discovered incidentally during the study (e.g., via optional Month 12 biopsy or standard of care biopsy) with no clinical suspicion of acute rejection will not be included in the assessment of the primary endpoint. Note that ascites-based dosing adjustment is not considered a rescue medication because the occurrence of ascites is not due to lack of efficacy. Accordingly, administering CFZ533 to compensate drug loss caused by ascites cannot be considered rescue medication. In addition, this unscheduled administration aims not to result in exposure higher than that seen in participants with no ascites.

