2.5.3 Handling of missing values/censoring/discontinuations

The primary analysis is based on the FAS. Since participants continue to be followed after early study drug discontinuation, the number of missing values is expected to be limited. In case of missing values,

- 1. For participants with death, a value of 0 will be imputed after the time of death.
- 2. Participants that are lost to follow-up or have missing assessments will have missing values assessed via MMRM assuming MAR.

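### The primary Poisson analysis ends at drug discontinuation, although the SAP states a treatment-policy estimand for it

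*SAP*

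**What the plan says.** **Estimand and general rule.** SAP 2.4.1 defines the treatment of interest "regardless of treatment or study discontinuation, loss to follow-up, ascites-based dosing adjustment, or administration of CS (treatment policy"). SAP 2.1 bases efficacy on "all available data including those after study medication discontinuation or as a supportive analysis based only on on-treatment values".

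**Method.** SAP 2.4.2 sets the expected count to a rate times t, with t "being the total on-treatment time in group" i. It ends each participant's follow-up at "min(upper limit of the Month 12 visit window, date of treatment discontinuation, date of lost-to-follow-up"), and says the resulting difference "will then be evaluated as for the primary estimand". SAP 2.4.3 adds: "Participants continued to be followed until Month 12 visit, early study drug discontinuation, or lost to follow-up, whichever first". Participants without an event are treated as censored.

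**Follow-up elsewhere.** SAP 2.5.3, on eGFR, says: "Since participants continue to be followed after early study drug discontinuation, the number of missing values is expected to be limited". Protocol section 8 expects all randomized participants to stay in the study to Month 24 even off treatment. Protocol 12.4.3 bases the primary analysis on observations both on and off treatment.

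**Drug-stop date.** SAP 2.4.2 uses the CFZ533 stop plus 14 days in Arms 2 and 3. For control it repeats the rule from protocol 12.4.4: "Arm 1: earliest date of discontinuation of study drug (TAC or MMF"). The follow-up formula in protocol 12.4.4 has no drug-stop term. SAP 2.1.1 ends control treatment at the last TAC dose.

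**Disclosure.** SAP 2.1 and 2.4 say the analysis was modified because of early termination. SAP section 4 records no change from the protocol. SAP 2.13 refers to 2.4.4 for the Poisson details, but 2.4.4 says only that no sensitivity analysis is planned.

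**The concern.** The estimand asks what happens by Month 12 whether or not drug is stopped. The method asks what happens while on drug. The two agree only in special cases, for example when the failure hazard is constant and does not change after stopping.

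Read with 2.4.3, any BPAR, graft loss or death after the cut-off is left out of the 15%/80% rule. A rejection that itself triggers the stop should normally be biopsied within 48 hours (protocol 6.6.2) and so already be counted; the loss concerns later failures.

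The cut-off also differs by arm. Protocol 6.5.2 allows MMF to be dropped completely while randomized treatment continues. An MMF stop then ends the clock for a control participant but not for a CFZ533 participant.

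A separate point is that the 2.4.2 formula has no term for the event date, so a participant who fails keeps accruing person-time. Taken literally this understates the rates, and it differs from the SAP's own exposure-adjusted method in 5.5.1, which stops at the first event.

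The study is terminated and the documents contain no result. What is at stake is the meaning of the primary number in the abbreviated CSR.

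**Working it through.** **1. The plan's own figures.** I enumerated Binomial(48, p1) × Binomial(32, p0) with Beta(1/3, 1/3) priors and success if P(difference < 0.15 | data) > 0.8. All 15 rows of SAP Table 3-2 reproduce to within 0.001, e.g. 0.9040 against 0.904 (0.11 vs 0.103) and 0.7295 against 0.729 (0.15 vs 0.103). The table assumes complete binomial follow-up, not the on-treatment Poisson model now planned.

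**2. A case that can be checked by hand.** Assume constant hazards over one year and person-time ending at the event.
- On-drug failure 10%: a = −ln 0.90 = 0.1054.
- CFZ533 discontinuation 30%: d = −ln 0.70 = 0.3567.
- Off-drug hazard three times on-drug: b = 3a = 0.3161.

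Treatment-policy failure = 1 − [exp(−(a+d)) + d·exp(−b)·(1 − exp(−c))/c], with c = a + d − b = 0.1460. This gives 1 − [0.630 + 0.3567 × 0.7290 × 0.9305] = 1 − [0.630 + 0.242] = 0.128.

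The on-treatment model returns 1 − exp(−a) = 0.100. With control at 10% (10% stopping, hazard unchanged), the true excess is 2.8 points and the on-treatment excess is 0.

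If off-drug events are counted but divided by on-drug time, mean time is 0.370/0.4620 = 0.801 and the result is 1 − exp(−0.128/0.801) = 0.148. That matches neither target.

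**3. The decision rule at 48 vs 32.**

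From the documents: the 15%/80% rule, Gamma(0.001, 0.001) priors and θ = 1 − exp(−λ) (SAP 2.4.2); Day 358 as the end of the Month 12 window (SAP 5.1), so at most 357 days; the 14-day lag for CFZ533; on-drug 12-month failure of 15% vs 10.3% (a Table 3-2 row).

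Assumed: 30% of CFZ533 and 10% of control stop, at uniform times independent of failure; off-drug hazard is k times on-drug in both arms; hazard is either constant or early-weighted (70% of on-drug failures by Day 90).

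Each Poisson version estimates θ = 1 − exp(−D/T), with D failures and T years:
- *Written*: on-drug events over time to the cut-off (the 2.4.2 formula).
- *Event*: the same, with time ending at the event.
- *Full*: all events over time to event or Day 358.

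The true excess is the difference in the proportions failing by Day 358. Expected excesses use 2,000,000 participants per arm. Success probabilities use 20,000 trials (Monte Carlo SE at most 0.4 points).

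| Hazard | k | Excess in points: true / written / event / full | Success %: written / event / full |
|---|---|---|---|
| Constant | 1 | 4.7 / 4.3 / 4.8 / 4.8 | 77 / 70 / 72 |
| Constant | 2 | 6.0 / 4.2 / 4.8 / 6.1 | 76 / 70 / 64 |
| Constant | 3 | 7.2 / 4.3 / 4.8 / 7.3 | 76 / 70 / 57 |
| Early | 1 | 4.7 / 5.0 / 5.9 / 5.0 | 72 / 63 / 71 |
| Early | 2 | 5.4 / 5.0 / 5.8 / 5.7 | 72 / 63 / 66 |
| Early | 3 | 6.1 / 5.0 / 5.9 / 6.5 | 71 / 63 / 62 |

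- **Drug-stop cut-off alone** (event minus full): −2, +6, +13 points of success probability for k = 1, 2, 3 (constant); −8, −3, +1 (early).
- **Person-time not ending at the event** (written minus event): 6 to 9 points. This is an upper bound, since it treats every failure as staying on drug, while death and graft loss end dosing.
- **CFZ533 failures after the cut-off:** 1.0 to 2.6 of 48 (constant), 0.5 to 1.4 of 48 (early).
- **Only the CFZ533 hazard rises** (constant, k = 3): true excess 8.1 against 4.2 written; success 76% written, 53% full.
- **Reversal** (20% of CFZ533 and 40% of control cut off, constant, k = 3): true excess 3.4 against 4.2 written; success 75% written, 73% full.

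**4. The other reading** (all events over on-drug time) overstates the excess by about 1.1 points in all six base cases. The sign depends on the stop pattern: with 20% stopping in both arms (constant, k = 1) it gives 4.5 against a true 4.7, and in the reversal case about 1.5 against 3.4.

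**The case against.** **On-treatment may be intended.** SAP 2.4.2 says so in its exposure term, and SAP 2.13 has the interim endpoints analysed as in the full CSR using on-treatment data. On that view only the label in 2.4.1 needs changing. This stands as a possible repair, but it concedes that the estimand and the method disagree. SAP 2.1 would need changing too.

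**SAP 2.4.3 may define an analysis window, not trial conduct.** That is a fair reading and softens the clash with 2.5.3, which sits in the eGFR section. The clash with 2.4.1 and 2.1 remains.

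**The control-clock conflict is softer than it looks.** The lead-in to the definitions in 2.1.1 leaves their scope unclear, and 2.4.2 states its own rule. The different treatment of an MMF stop in the two arms remains.

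**The person-time point is ambiguous.** Calling event-free participants censored suggests that an event ends follow-up, and the protocol 12.4.4 formula has the same omission. The formula should still say so.

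**The figures depend on chosen inputs.** They do. With the 0.11 vs 0.103 row, early-weighted hazard and the same stops, success is about 89 vs 89%, 90 vs 87% and 88 vs 85% (written vs full) for k = 1, 2, 3. With 20% stopping in both arms (15% vs 10.3%), the written excess is within about 1 point of the truth for k up to 3. Under the early-weighted hazard the full version also misses the truth, by 0.3 to 0.4 points.

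**Little hangs on it now.** Development in this disease area has stopped, and the Kaplan-Meier analysis in 2.4.5 keeps off-drug failures, with 95% intervals. But the 15%/80% rule is not applied to it, so no planned analysis applies the rule to the stated estimand.

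**Conclusion.** The concern holds. SAP 2.4.1 and 2.1 state one target, and 2.4.2 and 2.4.3 compute another under the first one's name. Early termination explains the departure from the protocol but not this internal conflict.

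Confidence is high for the conflict in the text and does not extend to the size or direction of the bias. In the assumed scenarios, the cut-off at drug stop moves the probability of success by between −8 and +13 points. It understates the CFZ533 excess if CFZ533 participants stop more often and then fail faster. It can reverse if many controls are cut off at an MMF stop. The unclear end of person-time adds up to a further 6 to 9 points. This should be fixed before the primary result is reported.

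**What to change.** In SAP 2.4.2 and 2.4.3:
- Count every BPAR, graft loss and death up to Day 358, on or off drug.
- Measure time from randomization to the earliest of event, Day 358 or last contact, and remove the treatment-discontinuation term.
- Keep the on-treatment version as a labelled supplementary analysis, with its control cut-off reconciled with SAP 2.1.1.
- Record the change from the protocol's binomial primary analysis in section 4, and correct the cross-reference in 2.13.

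If the sponsor does intend an on-treatment analysis, restate 2.4.1 accordingly, bring 2.1 into line, and report the all-follow-up version of the 15%/80% rule beside it.

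The cost is SAP wording and one rerun of the Poisson model on follow-up the protocol already schedules. Where termination cut follow-up short, censor at last contact.
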